A dose-limiting toxicity (DLT) will be defined as any one of the following adverse events occurring within 6 weeks from last dose of radiation therapy for radiotherapy phase and 4 weeks from the start day of maintenance dose of vorinostat [Cycle 1 Day 43 (+/-3)] for maintenance phase:

CNS toxicities:

Acute CNS toxicities (occurring \leq 30 days after completing radiation therapy):

 Any grade 3 or higher central nervous adverse events including but not limited to headache, dizziness, vertigo, new onset seizures, cerebral edema, cerebral hemorrhage, and new onset neurologic deficit.

Delayed onset CNS toxicities (occurring >30 days after completing radiation therapy):

• Any grade 3 or 4 adverse event arising within the irradiated volume including but not limited to focal neurological deficits.

Non-CNS toxicities:

- Any Grade 4 immune-related adverse event (irAE)
- Any \geq Grade 3 colitis
- Any Grade 3 or 4 non-infectious pneumonitis irrespective of duration
- Any Grade 2 pneumonitis that does not resolve to ≤ Grade 1 within 3 days of the initiation of maximal supportive care
- Any Grade 3 irAE, excluding colitis or pneumonitis, that does not downgrade to Grade 2 within 3 days after onset of the event despite optimal medical management including systemic corticosteroids or does not downgrade to ≤ Grade 1 or baseline within 14 days
- Liver transaminase elevation > 8 × upper limit of normal (ULN) or total bilirubin > 5 × ULN
- Any \geq Grade 3 non-irAE, except for the exclusions listed below

The definition excludes the following conditions:

- Grade 3 fatigue lasting ≤ 7 days
- Grade 3 endocrine disorder (thyroid, pituitary, and/or adrenal insufficiency) that is managed with or without systemic corticosteroid therapy and/or hormone replacement therapy and the subject is asymptomatic
- Grade 3 inflammatory reaction attributed to a local antitumor response (eg, inflammatory reaction)
- Concurrent vitiligo or alopecia of any AE grade

- Grade 3 infusion-related reaction (first occurrence and in the absence of steroid prophylaxis) that resolves within 6 hours with appropriate clinical management
- Grade 3 or 4 neutropenia that is not associated with fever or systemic infection that improves by at least 1 grade within 14 days. Grade 3 or Grade 4 febrile neutropenia will be a DLT regardless of duration or reversibility
- Grade 3 or 4 lymphopenia

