- Grade 3 or 4 thrombocytopenia that is not associated with clinically significant bleeding that requires medical intervention, and improves by at least 1 grade within 14 days
- Isolated Grade 3 electrolyte abnormalities that are not associated with clinical signs or symptoms and are reversed with appropriate maximal medical intervention within 3 days
- Immune-related AEs are defined as AEs of an immune nature (ie, inflammatory) in the absence of a clear alternative etiology. In the absence of a clinically significant abnormality, repeat laboratory testing will be conducted to confirm significant laboratory findings prior to designation as a DLT. Laboratory abnormalities that are not deemed to be clinical significant will not be considered a DLT.

While the rules for adjudicating DLTs in the context of dose exploration are specified above, an AE not listed above may be defined as a DLT after a consultation with the sponsor and investigators, based on the emerging safety profile.

Dose escalation will be determined based on the occurrence of DLTs. For the purposes of determining whether to advance the dose levels, DLTs will be counted by patient. For all observed toxicities, subjects should be assessed for inter-current illness or other causes and treated as appropriate.

In the event of the development of any grade 3 or 4 toxicity felt to be at least possibly related to pembrolizumab, pembrolizumab will be held until resolution to grade 1 or baseline assuming that occurs within 6 weeks window. Treatment with pembrolizumab can be resumed after resolution of DLT to grade 1 or baseline except for following adverse events: Grade 4 infusion reactions, \geq Grade 3 pneumonitis, \geq Grade 3 nephritis, \geq Grade 3 colitis, increased alanine aminotransferase (ALT) or aspartate aminotransferase (AST) greater than 5 times upper limit of normal or total bilirubin greater than 3 times upper limit of normal.

Dose escalation for vorinostat will follow the standard 3+3 design. The enrollment to expansion cohort for radiotherapy phase will be delayed for 6 weeks after the completion of radiation therapy by the last patient enrolled at the MTD dose level for radiation therapy phase. The enrollment to expansion cohort for maintenance phase will be delayed for 4 weeks after the start day of maintenance dose of vorinostat [Cycle 1 Day 43 (+/-3)] by the

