last patient enrolled at the MTD dose level for maintenance phase. This period will allow monitoring potential delayed toxicities. Dose escalation/de-escalation will proceed according to the following scheme.

Table 3 Dose Escalation Decision Rule

Number of Patients with DLT at a Given Dose Level	Escalation Decision Rule	
0 out of 3	Enter 3 patients at the next dose level.	
≥ 2	Dose escalation will be stopped. This dose level will be declared the maximally administered dose (highest dose administered). Three (3) additional patients will be entered at the next lowest dose level if only 3 patients were treated previously at that dose.	
1 out of 3 or ≥ 2 grade 2 CNS toxicities	 Enter at least 3 more patients at this dose level. If 0 of these 3 patients experience DLT, proceed to the expansion cohort. If 1 or more of this group suffer DLT, then dose escalation is stopped, and this dose is declared the maximally administered dose. Three (3) additional patients will be entered at the next lowest dose level if only 3 patients were treated previously at that dose. 	
≤1 out of 6 at highest dose level below the maximally administered dose	This is the dose to be used in the expanded cohort and will be considered recommended phase 2 dose.	

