5.9 Subject Replacement Strategy

In dose escalation phase, subject will be replaced if they are considered inevaluable. A subjects will be considered DLT-evaluable if they have incurred a DLT within a DLT evaluation period or meet all of the following criteria: a) have received at least 85% of the prescribed doses of vorinostat, b) have received at least 85% of the prescribed doses of pembrolizumab, and c) have received the full dose (60 Gy) of radiation.

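### No text requires a patient to be observed to the end of the DLT window before counting as DLT-free in a dose-level or MTD decision

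*Combined protocol and SAP*

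**What the plan says.** Four pieces of text bear on this.

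- **DLT window (5.3.1).** A DLT is an event "occurring within 6 weeks from last dose of radiation therapy for radiotherapy phase", or within "4 weeks from the start day of maintenance dose of vorinostat" for the maintenance phase. One category, "Delayed onset CNS toxicities (occurring >30 days after completing radiation therapy"), can by definition arise only late.
- **Decision rule (5.3.1, Table 3, Dose Escalation Decision Rule).** With 0 of 3 DLTs the instruction is "Enter 3 patients at the next dose level". No row states when DLTs are counted, and none mentions evaluability or a completed window. The text before the table says that escalation is based on DLT occurrence and follows a standard 3+3 design.
- **Written wait (5.3.1).** "The enrollment to expansion cohort for radiotherapy phase will be delayed for 6 weeks after the completion of radiation therapy by the last patient enrolled"; the patient meant is the last one treated at the level taken as the MTD. A parallel sentence sets 4 weeks from the start of maintenance vorinostat. Both sentences concern expansion entry only, and the reason given is to watch for delayed toxicity.
- **Evaluability (5.9).** "A subjects will be considered DLT-evaluable if they have incurred a DLT within a DLT evaluation period or meet all of the following criteria": 85% of vorinostat doses, 85% of pembrolizumab doses, and the full 60 Gy. No minimum follow-up is listed, and the period over which the 85% is measured is not given.

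**The concern.** The MTD is the primary objective (3.1), and the DLT count in Table 3 determines it. A DLT-free patient should add a zero to that count only once the whole window has been observed. Section 5.9 is the only place that says which DLT-free patients are evaluable, and its conditions concern dosing, not observation. Two things follow.

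- A patient who has had enough drug and radiation, then withdraws or is lost before the window closes, is evaluable, is not replaced, and counts as DLT-free.
- Nothing written stops a Table 3 step from being taken while part of the window is still unobserved.

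Both effects go in the same direction: unobserved time is treated as toxicity-free, which makes a level look safer than it is. The late part of the window matters in this trial. Section 5.2.2.2 expects transient neurological worsening 1-3 months after radiotherapy, and the delayed-onset CNS category begins only after day 30.

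**Working it through.** The documents give no figure on this point to reproduce. The check is a dosing calendar followed by an illustration.

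**Inputs.** 30 daily fractions (5.3); pembrolizumab on D1, D22, D43 and D64 (6.1); vorinostat on days 1-5 weekly during radiotherapy, then one week on and one week off from about D43 (5.3, 5.3.1); the windows in 5.3.1; the criteria in 5.9. Assumptions: D1 is a Monday and no fraction is missed.

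**When the windows close.**
- Radiotherapy phase: last fraction D40; 40 + 42 = D82. If radiotherapy ends on D47, D89.
- Maintenance phase: 43 + 28 = D71 (+/-3).

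**When 5.9 can first be met.** Doses needed = 0.85 x prescribed, rounded up.

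| Phase and denominator | Vorinostat | Pembrolizumab | All criteria met | Gap to closure |
|---|---|---|---|---|
| Radiotherapy, radiotherapy-phase doses | 26 of 30, D36 | 2 of 2, D22 | D40 (60 Gy) | 82 - 40 = 42 days |
| Radiotherapy, whole-window doses | 44 of 51, D63 | 4 of 4, D64 | D64 | 82 - 64 = 18 days |
| Maintenance, doses in that window | 12 of 14, D61 | 2 of 2, D64 | D64 | 71 - 64 = 7 days |

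The 60 Gy criterion is already met when the maintenance window opens. In the radiotherapy phase even the later date, D64, is only 64 - 40 = 24 days after the last fraction, before the delayed-onset CNS category can start.

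**Effect on a 0-of-3 result (radiotherapy ladder, decision at the third patient's last fraction).** Assume a true DLT rate p = 0.33, with a share f of DLTs falling after the last fraction.

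- Full windows: (1 - p)^3 = 0.67^3 = 0.30.
- All three finish together, nothing observed after radiotherapy: (1 - p(1 - f))^3. For f = 0.25, 0.7525^3 = 0.43. For f = 0.50, 0.835^3 = 0.58.
- Even accrual of 32 patients over 24 months (1.0): spacing (24/32) x 30.44 = 22.8 days. When the third patient finishes, the three have 45.7, 22.8 and 0 days behind them, or 100%, 54% and 0% of a 42-day window. With late DLTs spread evenly over the window:
  - f = 0.25: 0.67 x (1 - 0.33(1 - 0.25 x 0.46)) x 0.7525 = 0.67 x 0.708 x 0.7525 = 0.36.
  - f = 0.50: 0.67 x (1 - 0.33(1 - 0.50 x 0.46)) x 0.835 = 0.67 x 0.746 x 0.835 = 0.42.

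**Effect of one patient lost in the gap.** For a patient who is DLT-free at the last fraction and lost then, for reasons unrelated to toxicity, the chance that a DLT within the window goes unseen is pf / (1 - p(1 - f)): 0.0825/0.7525 = 0.11 for f = 0.25, and 0.165/0.835 = 0.20 for f = 0.50.

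**The case against.** The strongest reply is that the documents are silent here, not permissive. Table 3 never mentions evaluability, 5.9 is a replacement rule, escalation rests on DLTs that are themselves defined by the window, and a standard 3+3 design is naturally read as waiting for completed windows. This stands. A reader might infer that the protocol authorises clearing a level at the last fraction. It does not say so, and nothing shows that anyone escalated early.

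The reply also limits the size in four ways.

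- The 6-week gap depends on reading the 85% denominators as radiotherapy-phase doses, which 5.9 does not specify.
- Section 5.3 reports the radiotherapy ladder already reduced to level -1 and being expanded, and maintenance escalated to 400 mg/day, the top level in its schedule. Little upward escalation appears to remain.
- A reader might calculate the chance of clearing a level as 0 of 3, or 1 of 3 then 0 of 3, which gives 43% with full windows and 61-78% with none of the post-radiotherapy time observed. That overstates the effect. The second path goes to expansion, where the written hold applies, and the trial's own accrual rate would leave some of the window observed.
- A late DLT in a patient still being followed can be added to the count before expansion opens, so early steps need not corrupt the final MTD.

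The last argument does not reach the patient who has left follow-up. The hold is a calendar wait tied to the last patient enrolled. It does not recover missing observation, and 5.9 does not call for replacement.

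**Conclusion.** The point holds as a gap in the rule for who counts and when. No text requires the DLT window to be complete before a Table 3 step, and 5.9 accepts a DLT-free patient on dosing alone. The gap is up to 42 days or about 18 days in the radiotherapy phase, depending on an undefined denominator, and about 7 days in maintenance.

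The rise in the chance of 0 of 3, from 0.30 to about 0.36-0.42 (even accrual) or 0.43-0.58 (all three finishing together), rests on an assumed 33% DLT rate and an assumed 25-50% late share. The documents supply neither. It illustrates the rule on the radiotherapy ladder and does not forecast what remains of this trial. Given where both ladders stand, the main remaining effect is on which patients count towards the MTD, and on any entry at the same or a lower level. That the MTD has actually been set too high is not something the documents support.

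**What to change.** - **Section 5.9:** add a criterion that a DLT-free patient has been observed to the end of the protocol's own DLT window for the phase in question. State the period over which the 85% of vorinostat and pembrolizumab doses is measured, separately for each phase.
- **Table 3 (Dose Escalation Decision Rule):** state that a patient counts in an escalation or MTD decision only after having a DLT or completing that window, and reconcile this with the window definition and the expansion hold in 5.3.1.

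This takes a few sentences and introduces no new window, dose or clinical rule. On the calendar above, the earliest decision becomes about D82 in the radiotherapy phase (D89 if radiotherapy ends on D47) and about D71 (+/-3) in maintenance. The cost is a short wait between cohorts, of the kind already accepted before expansion, and possibly a few more replaced patients. If the site already waits, the change only records its practice.

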5.3 Trial Treatments

Treatment must begin within 21 days of registering to the trial. Treatment should also begin ≥ 3 weeks and ≤ 6 (+/1) weeks following surgery. Each cycle will consist of 12 weeks.

Dose Escalation Cohort:

Treatment will include two phases: 1) concurrent radiotherapy phase and 2) maintenance phase. Dose escalation will occur separately for concurrent radiotherapy part of treatment and maintenance part of treatment.

The dose of pembrolizumab will be 200 mg dose IV every 3 weeks. The starting dose (i.e., dose level 1) of vorinostat was 200 mg/day orally on days 1-5 every week during radiotherapy and 300 mg/day orally 1 week on 1 week off during maintenance phase, starting after completion of concurrent therapy with radiation (+/- 3 days). The dose of vorinostat during radiotherapy was reduced to 100 mg mg/day orally on days 1-5 every week due to DLT. This dose is well tolerated and is currently being expanded.

The starting dose of vorinostat during maintenance phase, beginning after completion of concurrent therapy with radiation (+/- 3 days) was 300 mg/day orally 1 week on 1 week off. The dose is escalated to 400 mg/day orally 1 week on 1 week off, as per schema in a 3+3 fashion.

Concurrent Radiotherapy Phase:

During concurrent radiotherapy phase of treatment, patients with newly diagnosed GBM will receive radiotherapy (60 Gy in 30 daily fractions) as mentioned above.

Temozolomide (75 mg/m²/day orally) will be administered daily during the course of radiotherapy as per standard of care [22]. Temozolomide will be administered continuously from Day 1 of radiotherapy to the last day of radiation at a daily oral dose of 75 mg/m2. The dose will be determined using actual body surface area (BSA) as calculated in square meters at the beginning of the concomitant treatment. The BSA will be calculated from the height obtained at the screening visit and the weight obtained at the visit immediately before the first day of treatment. The dose of temozolomide does not have to be adjusted unless there has been at least a 10% change in body weight; recalculation of dose for < 10% weight changes is allowed at the discretion of the Investigator. The daily dose will be rounded to the nearest 5 mg.

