Vorinostat will be administered orally at 200, 300 or 400 mg/day (based on dose level) on a 1 week on 1 week off schedule for 12 months. Vorinostat will start the day after completion of radiotherapy (+ 3 days). Safety of vorinostat 400 mg/day on a 1 week on 1 week off schedule in combination with maintenance temozolomide has been shown in a phase 1 study by Lee et al. 2012 [34].

Pembrolizumab 200 mg IV will continue every 3 weeks (+/-3 days) for 12 months or 18 infusions whatever comes first

Table 3 summarizes the doses for pembrolizumab and vorinostat during maintenance part of treatment.

Table 3 Dose Escalation Schedule for Pembrolizumab and Vorinostat maintenance part of treatment.

	Dose Escalation Schedule During Maintenance Phase					
Dose Level	Dose					
	Pembrolizumab	Vorinostat				
Level -1	200 mg IV every 3 weeks	200 mg/day orally 1 week on 1 week off after radiotherapy				
Level 1	200 mg IV every 3 weeks	300 mg/day orally 1 week on 1 week off after radiotherapy				
Level 2	200 mg IV every 3 weeks	400 mg/day orally 1 week on 1 week off after radiotherapy				

In all patients, treatment with study drugs will continue until confirmed disease progression, patient refusal, patient lost to follow up, unacceptable toxicity, completion of scheduled dosing, whichever occurs first, or the study is terminated by the Sponsor (Moffitt Cancer Center).

Dose Expansion Phase:

The vorinostat doses used in the dose expansion cohort will be MTD determined from the dose escalation phase.

Definition of Maximum Tolerated Dose:

The maximum tolerated dose (MTD) is the highest dose of vorinostat in combination with pembrolizumab, temozolomide during and after radiation therapy that does not cause unacceptable toxicity in more than one of six patients at that dose level. The MTD is defined as one dose level below the highest toxic dose (i.e., the DLT dose).

Details on preparation and administration of pembrolizumab (MK-3475) are provided in the Pharmacy Manual.

5.3.1 5.3.1 Definition of Dose-Limiting Toxicity

Toxicities will be graded in severity according to the guidelines outlined in the NCI-CTCAE version 4.0. Dose limiting CNS and non-CNS toxicities will be defined differently and will be based on events that occur during the study period. In order to be declared as dose-limiting toxicity, an adverse event must be related to pembrolizumab and/or vorinostat.

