8.0 STATISTICAL ANALYSIS PLAN

8.1 Statistical Analysis Plan Summary

The number of patients for the dose escalation cohort will depend on the safety of dose level 1. There are two dose escalation levels and therefore the maximum sample size for the dose escalation cohorts will be 12 patients. In the dose expansion cohort, a total of 20 evaluable patients will be enrolled to confirm the safety at this dose and assess response to treatment. Therefore, the maximum sample size of the study is 32 patients. The sample size of 26 patients in treated at the MTD dose (20+3 patients from dose expansion cohort and 6+/-3 patients from the dose escalation) will give a two-sided 95% confidence interval (95%CI) of 39% to 79% for a 12-month overall survival rate of 60% when there is no censored data. If the 12-months overall survival rate increases to 80%, the corresponding 95%CI will be 60% to 93%. A two-sided 95% confidence interval for the median overall survival time is from 10 months to 23 months when the estimate of median overall survival time is 14.6 months and the percent censoring is anticipated to be 10%. These results assume Type-II Censoring and an exponential distribution of overall survival times with mean survival time of 21 months.

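### The rules that produce the MTD do not lead to one executable decision for every outcome, most plainly after 0/3 DLTs at the last dose level

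*Combined protocol and SAP*

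**What the plan says.** Section 5.3 sets out two vorinostat ladders, one for radiotherapy and one for maintenance, each with Levels -1, 1 and 2. Section 5.3.1 gives the decision table (headed Table 3, a number also used for the maintenance dose schedule). Its rows, from the top, are:

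- Row 1, 0 of 3 with DLT: "Enter 3 patients at the next dose level".
- Row 2, two or more DLTs: escalation stops, the level becomes the maximally administered dose, and the level below is filled to six.
- Row 3, 1 of 3 with DLT, or two or more grade 2 CNS toxicities: at least three more patients at the same level. No DLT among them leads to expansion; one or more makes the level the maximally administered dose.
- Row 4, at most 1 "out of 6 at highest dose level below the maximally administered dose": this is the expansion and recommended phase 2 dose.

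The MTD definition in Section 5.3 has two sentences. The first takes the highest dose "that does not cause unacceptable toxicity in more than one of six patients at that dose level". The second reads: "The MTD is defined as one dose level below the highest toxic dose (i.e., the DLT dose"). The result fixes the next stage: "The vorinostat doses used in the dose expansion cohort will be MTD determined from the dose escalation phase".

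On maintenance, Section 5.3 reports: "The dose is escalated to 400 mg/day orally 1 week on 1 week off, as per schema in a 3+3 fashion". The radiotherapy ladder has already been reduced to Level -1. On numbers, Section 8.1 says: "There are two dose escalation levels and therefore the maximum sample size for the dose escalation cohorts will be 12 patients". It puts 26 patients at the MTD, described as 20+3 from expansion and 6+/-3 from escalation.

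**The concern.** The MTD is part of the primary objective (Section 3.1) and sets the dose for the 20-patient expansion. The rule that produces it should give one decision for each possible result. Three results fail that test.

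1. **0/3 at Level 2.** Row 1 sends patients to a level that does not exist. Row 4 and the second MTD sentence both need a toxic dose above. The first MTD sentence counts six patients, and no rule adds three after 0/3. A less clean result at the same level, 1/3 then 0/3, does have a decision (expansion, by row 3).
2. **Level 2 toxic, then 2 or more of 6 DLTs at Level 1.** The second MTD sentence, read literally, names Level 1. The first sentence and row 4 exclude it.
3. **0/3 DLTs with two or more grade 2 CNS toxicities.** Row 1 and row 3 are both met and give different instructions.

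The stake is that the primary result could rest on a choice made after the data are seen.

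**Working it through.** **The plan's own figures.** Escalation maximum: 2 levels x 6 = 12. Study maximum: 12 + 20 = 32. Exact (Clopper-Pearson) 95% intervals with n = 26: 39.1% to 78.5% at 60% survival and 59.8% to 93.0% at 80%, matching the stated 39% to 79% and 60% to 93%. The arithmetic in Section 8.1 therefore reproduces; the problem is in the decision rules.

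**Outcomes at Level 2, taken through the table**

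| Outcome at Level 2 | Row | Decision in the text |
|---|---|---|
| 0/3 | 1 | Next level: none exists |
| 1/3, then 0/3 | 3 | Expansion |
| 1/3, then 1 or more | 3 | Maximally administered dose; fill the level below |
| 2 or more of 3 | 2 | Maximally administered dose; fill the level below |

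**How often, and what three versus six changes.** The documents give no DLT rates, so p = 10, 20, 30 and 40% are assumed, with independent patients, cohorts of exactly three, and the grade 2 CNS trigger ignored. Let q = 1 - p.

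- P(0/3) = q^3
- P(1/3 then 0/3) = 3pq^2 x q^3 = 3pq^5
- Level 2 accepted if three clean patients suffice: q^3 + 3pq^5
- Level 2 accepted if at most 1/6 is required: q^3(q^3 + 3pq^2) + 3pq^5
- Difference: q^3(3p^2q + p^3)

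| p | P(0/3) | P(1/3, 0/3) | Accepted, three suffice | Accepted, six required | Difference |
|---|---|---|---|---|---|
| 10% | 0.729 | 0.177 | 0.906 | 0.886 | 0.020 |
| 20% | 0.512 | 0.197 | 0.709 | 0.655 | 0.053 |
| 30% | 0.343 | 0.151 | 0.494 | 0.420 | 0.074 |
| 40% | 0.216 | 0.093 | 0.309 | 0.233 | 0.076 |

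**Conflict between the two MTD sentences.** Under the table, Level 2 opens only after 0/3 at Level 1, because 1/3 then 0/3 at Level 1 goes to expansion. So 2 or more of 6 at Level 1 requires 2 or more DLTs among the three patients added there. Per opening of Level 2, the probability is P(Level 2 toxic at p2) x P(2 or more of 3 at p1). The first factor is 1 minus the acceptance probability above; the second is 3p1^2(1 - p1) + p1^3.

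| p1 / p2 | Three suffice | Six required |
|---|---|---|
| 10% / 20% | 0.291 x 0.028 = 0.008 | 0.345 x 0.028 = 0.010 |
| 20% / 30% | 0.506 x 0.104 = 0.053 | 0.580 x 0.104 = 0.060 |
| 30% / 40% | 0.691 x 0.216 = 0.149 | 0.767 x 0.216 = 0.166 |

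**Rows 1 and 3 together.** Section 5.3.1 bases escalation on DLTs, and its CNS DLTs start at grade 3. Grade 2 CNS toxicities are therefore not listed DLTs, and a cohort can meet both rows. How often cannot be derived from the documents.

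**Survival precision.** Section 8.1 can be read as 20 + 6 = 26 or as 23 + 3 = 26. On either, the interval at 60% is unchanged. If instead three escalation patients joined only 20 in expansion (an assumption), n = 23 gives 37.7% to 79.6%.

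**The case against.** The best defence is that nobody would be misdosed. After 0/3 at Level 2 no rule names any other dose, the first MTD sentence points to Level 2, and both ladders stop there by design. That stands. A reader might infer that patients could be sent above Level 2, or that every tolerated result there lacks a decision. The text supports neither: there is no higher level to assign, and 1/3 then 0/3 goes to expansion. Nor does a tolerated Level 2 become the maximally administered dose merely by being the highest given, since rows 2 and 3 declare that dose only after excess DLTs.

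A second defence is that Section 8.1, by allowing 6 minus 3 escalation patients, already contemplates three at the MTD. That is a fair reading, but the sentence is garbled, is compatible with three or six, and sets no decision rule. The label of a standard 3+3 design (Sections 2.1 and 5.3.1) does not supply the number either, and Section 5.3.1 makes its own table govern.

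Third, the conflicts need a literal reading. Row 2, row 4 and the first MTD sentence agree against Level 1, and row 3, as the more specific row, probably governs the CNS case. Both are likely resolutions, but the protocol states neither.

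Finally, the expansion hold in Section 5.3.1 runs from the last patient at the MTD level. Whether that is the third or the sixth follows from the same open question; it is not a separate gap.

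**Conclusion.** The point holds as a should-fix. The rules for the MTD are not executable after 0/3 at the last level, and they conflict in two other situations. Under the assumed DLT rates, the outcome without an executable rule arises in 73, 51, 34 and 22% of Level 2 openings. The consequence is modest: reading three or six as the requirement moves acceptance of Level 2 by about 2 to 8 percentage points. The conflict between the MTD sentences arises in about 1, 5 and 15% of openings at the assumed pairs of rates if three patients suffice (1, 6 and 17% if six are required).

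A reader might also infer that the survival estimate loses precision. It does so negligibly, and not at all if the total stays at 26.

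The matter concerns the maintenance ladder, which Section 5.3 suggests has reached Level 2 or is heading there. The wording does not show that 0/3 has been observed. The radiotherapy ladder stands at Level -1, so the last-level gap does not appear live there.

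**What to change.** Reconcile the MTD definition in Section 5.3, the DLT-based escalation statement and decision table in Section 5.3.1, and the patient counts in Section 8.1, so that:

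- each outcome, including 0/3 at the last level, leads to one executable decision and one MTD;
- there is a single MTD definition;
- the number of evaluable patients required at the MTD is stated, and Section 8.1 agrees with it;
- the table says which row takes precedence when rows 1 and 3 both apply, and the escalation statement matches.

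The amendment should also say how decisions already taken under the present table are treated. The sponsor decides the content of each rule.

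The cost is a text amendment, plus up to three more patients at the last level if the sponsor chooses six. In that case the maintenance path is 3 at Level 1 + 6 at Level 2 = 9 patients, within the maximum of 12 if that figure is counted for this ladder alone.

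### The dose-escalation table gives the same 1/6 DLT count opposite outcomes, depending on whether three patients were added for a DLT or for Grade 2 CNS toxicities

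*Combined protocol and SAP*

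**What the plan says.** Two tables in Section 5.3 carry the number 3. This point concerns the Dose Escalation Decision Rule table in Section 5.3.1.

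- **Row 1**, for 0 of 3 patients with a DLT: "Enter 3 patients at the next dose level".
- **Row 2**, for two or more patients with a DLT: escalation stops and the level is the maximally administered dose.
- **Row 3**, for "1 out of 3 or ≥ 2 grade 2 CNS toxicities": at least three more patients enter at the same level. Then "If 0 of these 3 patients experience DLT, proceed to the expansion cohort"; otherwise "If 1 or more of this group suffer DLT, then dose escalation is stopped, and this dose is declared the maximally administered dose".
- **Row 4** takes the expansion dose and recommended phase 2 dose from a level with "≤1 out of 6 at highest dose level below the maximally administered dose".

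Section 5.3 defines the MTD as the highest vorinostat dose in the combination that "does not cause unacceptable toxicity in more than one of six patients at that dose level", and then as one level below the highest toxic (DLT) dose. Section 5.3.1 sets the acute CNS DLT threshold at Grade 3 or above. It bases escalation on DLTs, states that "DLTs will be counted by patient", and says that vorinostat escalation follows the standard 3+3 design. It requires a DLT to be related to pembrolizumab and/or vorinostat and to fall in a stated window.

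On current status, Section 5.3 says that the radiotherapy-phase dose was reduced to 100 mg/day (Level -1) and is being expanded. The maintenance dose has been escalated to 400 mg/day, which the maintenance schedule lists as Level 2, the top level.

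**The concern.** Row 3's follow-on rules suit a cohort that already has one DLT: one more makes at least 2/6, and none leaves 1/6. The row applies the same rules to a cohort that may have no DLT at all. One DLT among the added patients then gives only 1/6, yet the level is treated as 2/6 would be.

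Determining the MTD is the primary objective. If this path occurred at maintenance Level 2, row 4 would look for the expansion dose and recommended phase 2 dose below it, on a DLT count that the MTD definition accepts and that the other branch of the same row sends to expansion.

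The trigger is also loosely specified. It names toxicities where the DLT rule counts patients, and it states neither a relatedness condition nor a window. Section 5.2.2.1 lists headaches, seizures and weakness as potential acute effects of radiotherapy itself, so these omissions could affect whether the row applies.

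**Working it through.** **Reading check.** The table takes a level to six patients, reading the minimum of three added patients as exactly three. Two levels give 2 × 6 = 12, and 12 + 20 in expansion = 32. Both match Section 8.1.

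**When the Grade 2 clause matters.** With one DLT in three, row 3 applies anyway. With two or more, row 2 applies. The clause therefore has effect only at 0/3 DLTs, and only if it overrides row 1.

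**All paths at one level** (MAD = maximally administered dose):

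| DLTs in first 3 | Grade 2 CNS trigger | DLTs in next 3 | Total | Table outcome | Within one of six? |
|---|---|---|---|---|---|
| 0 | no | none added | 0/3 | next level | not applicable |
| 0 | yes | 0 | 0/6 | expansion | yes |
| **0** | **yes** | **1** | **1/6** | **MAD** | **yes** |
| 0 | yes | 2 or 3 | 2/6 or 3/6 | MAD | no |
| 1 | yes or no | 0 | 1/6 | expansion | yes |
| 1 | yes or no | 1 to 3 | 2/6 to 4/6 | MAD | no |
| 2 or 3 | yes or no | none added | 2/3 or 3/3 | MAD | no |

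The bold row is the only path on which a level within one of six is declared the MAD.

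**How often.** The documents give neither a DLT rate nor a Grade 2 CNS rate, so both are assumed. Let p be the DLT rate and q the probability that a patient without a DLT has a Grade 2 CNS event. Patients are independent, and the trigger is counted by patient (at least 2 of 3).

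For p = 0.10:

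- P(0/3 DLTs) = 0.9³ = 0.729, and P(1/3 DLTs) = 3 × 0.1 × 0.9² = 0.243.
- P(trigger) = 3q²(1 − q) + q³ = 0.104, 0.216 and 0.500 for q = 0.2, 0.3 and 0.5.
- P(0/3 and trigger) = 0.729 × P(trigger) = 0.076, 0.157 and 0.365.
- P(1/6, declared MAD) = the previous line × 0.243 = 0.018, 0.038 and 0.089.
- P(MAD, given 0/3 and trigger) = 1 − 0.729 = 0.271.

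For p = 0.20, P(0/3) = 0.8³ = 0.512 and P(1/3) = 3 × 0.2 × 0.8² = 0.384. The 1/6 path then has probability 0.020, 0.042 and 0.098 for the same q. Given the trigger at 0/3, the level is declared MAD with probability 1 − 0.512 = 0.488.

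**Effect on the level's label.** By the table, P(MAD) = P(2 or more of 3) + P(1/3) × [1 − P(0/3)] + P(0/3 and trigger) × [1 − P(0/3)]. If the one-of-six threshold governed, the last factor would be P(2 or more of 3). At p = 0.10, with P(2 or more of 3) = 0.028:

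| q | P(MAD), table as written | P(MAD), one of six governs |
|---|---|---|
| 0.2 | 0.114 | 0.096 |
| 0.3 | 0.137 | 0.098 |
| 0.5 | 0.193 | 0.104 |

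This comparison shows the size of the discrepancy, not which rule is right.

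**Secondary path.** At p = 0.10, the 0/6 path to expansion has probability 0.055, 0.115 and 0.266 for the three values of q. It leaves a question only where a higher level is untested.

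**The case against.** The best defence is that a CNS-specific brake may be deliberate in a trial combining new agents with brain irradiation. The MTD definition speaks of unacceptable toxicity and is tied to DLTs only through its second sentence. Section 5.3.1 also lets an unlisted event be called a DLT after consultation.

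That defence supports adding three patients, and the sponsor may well want the stricter outcome. It does not remove the inconsistency. If two patients with Grade 2 CNS events count as unacceptable toxicity, more than one of six is already affected, and sending 0/6 DLTs to expansion breaks the definition instead. The consultation clause works case by case and does not make Grade 2 events DLTs in general.

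Four stronger readings are tempting, but the documents do not support them.

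- *The Grade 2 clause is what ends escalation at 0/6.* The instruction to go to expansion does that, and it equally follows 1/3 then 0/3 with no Grade 2 event. At maintenance Level 2 there is no higher level to open.
- *Rows 1 and 3 give irreconcilable orders.* Precedence is unstated, but the Grade 2 clause has effect only if it overrides row 1, so that is the natural reading.
- *Two tumour headaches in one patient would trigger the row.* The column heading counts patients, and Section 5.3.1 asks that all toxicities be assessed for other causes. The wording leaves the possibility open, but this is its least favourable reading.
- *The table calls a 1/6 dose too toxic.* It calls it the highest dose administered. Row 4 then puts the recommended dose below it.

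**Conclusion.** The point holds in a narrow form. As written, row 3 makes the outcome at 1/6 DLTs depend on the order of events. One of the two outcomes does not fit the MTD definition, or the statements that escalation rests on DLTs counted by patient under a standard 3+3 design. The finding follows from the text if the Grade 2 clause overrides row 1 and exactly three patients are added.

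The conflict remains live for maintenance Level 2. It has little current bearing on the radiotherapy phase, which is in expansion at Level -1.

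The probabilities are illustrative, because they rest on assumed rates, independence and counting by patient. The conflicting path has probability of about 0.02 to 0.09 at a 10% DLT rate. Given the trigger at 0/3, the chance of the maximally administered label is 27%, or 49% at a 20% DLT rate. A reader might infer that the one-of-six threshold must prevail and the CNS rule be relaxed. The documents show only that the two texts disagree.

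**What to change.** Before the Level 2 maintenance decision, reconcile the MTD definition in Section 5.3, the escalation statements in Section 5.3.1 and the decision-rule table. Give the Grade 2 CNS trigger its own row, stating:

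1. what follows from each total DLT count in six patients, including whether a higher untested level opens after 0/6;
2. whether the row overrides row 1;
3. whether it counts patients or events;
4. whether the relatedness and window conditions for DLTs apply to it.

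If the stricter outcome at 1/6 is intended, amend the MTD definition to say so. Which rule governs is for the sponsor to decide. The cost is one table row or one amended definition, made by protocol amendment.
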